**10.8. Appendix 8: Values of Potential Clinical Importance**

As this is a placebo only device study there are no values of potential clinical importance.

## 10.9. Appendix 9: Abbreviations & Trade Marks

### 10.9.1. Abbreviations

Abbreviation	Description
A&R	Analysis and Reporting
AE	Adverse Event
CI	Confidence Interval
CSR	Clinical Study Report
DOB	Date of Birth
DP	Decimal Places
eCRF	Electronic Case Record Form
GSK	GlaxoSmithKline
ICH	International Conference on Harmonisation
IDSL	Integrated Data Standards Library
ITT	Intent-To-Treat
PDMP	Protocol Deviation Management Plan
QC	Quality Control
RAMOS	Randomization & Medication Ordering System
RAP	Reporting & Analysis Plan
SAC	Statistical Analysis Complete
SOP	Standard Operation Procedure
TFL	Tables, Figures & Listings

### 10.9.2. Trademarks

Trademarks of the GlaxoSmithKline Group of Companies
DISKUS
ELLIPTA

Trademarks not owned by the GlaxoSmithKline Group of Companies
HandiHaler
SAS

## 10.10. Appendix 10: List of Data Displays

### 10.10.1. Data Display Numbering

The following numbering will be applied for RAP generated displays:

Section	Tables	Figures
Study Population	1.1 to 1.n	1.1 to 1.n
Efficacy	2.1 to 2.n	2.1 to 2.n
Safety	3.1 to 3.n	3.1 to 3.n
Section	Listings	
ICH Listings	1 to x	
Other Listings	y to z	

### 10.10.2. Mock Example Shell Referencing

Non IDSL specifications will be referenced as indicated and if required example mock-up displays provided in [Appendix 11: Example Mock Shells for Data Displays](#).

Section	Figure	Table	Listing
Study Population	POP_Fn	POP_Tn	POP_Ln
Efficacy	EFF_Fn	EFF_Tn	EFF_Ln
Safety	SAFE_Fn	SAFE_Tn	SAFE_Ln

**NOTES:**

- Non-Standard displays are indicated in the 'IDSL / Example Shell' or 'Programming Notes' column as '[Non-Standard] + Reference.'

### 10.10.3. Deliverables

Delivery [Priority] 	Description
SAC [1]	Final Statistical Analysis Complete

**NOTES:**

1. Indicates priority (i.e. order) in which displays will be generated for the reporting effort

**10.10.4. Study Population Tables**

Study Population Tables					
No.	Population	IDSL / TST ID / Example Shell	Title	Programming Notes	Deliverable
Subject Disposition and Demography					
1.1.	ASE	IDSL_SP01	Summary of Subject Populations	Total column only	SAC
1.2.	ASE	IDSL_ES6	Summary of Screening Status and Reasons for Screen Failures		SAC
1.3.	ASE	IDSL_DM1	Summary of Age Ranges		SAC
1.4.	ITT	IDSL_SP02	Summary of Attendance at Each Clinic Visit	Total column only	SAC
1.5.	ITT	IDSL_SD1	Summary of Treatment Status and Reasons for Discontinuation of Study Treatment		SAC
1.6.	ITT	IDSL_ES1	Summary of End of Study Record		SAC
1.7.	ITT	IDSL_DM2	Summary of Demographic Characteristics		SAC
1.8.	ITT	IDSL_NS1	Summary of Number of Subjects by Centre		SAC
1.9.	ITT	IDSL_DM5	Summary of Race and Racial Combinations		SAC
1.10.	ITT	IDSL_DM6	Summary of Race and Racial Combination Details		SAC
1.11.	ITT	IDSL_TC1	Summary of Study Compliance	Show compliance on all three devices separately	SAC
Protocol Deviations					
1.12.	ITT	IDSL_SP04	Summary of Important Protocol Deviations		SAC
1.13.	ITT	IDSL_IE1	Summary of Inclusion/ Exclusion/ Randomisation Criteria Deviations for Intent-to-treat	Include both high level and lower level categories	SAC

Study Population Tables					
No.	Population	IDSL / TST ID / Example Shell	Title	Programming Notes	Deliverable
Medical Condition & Concomitant Medications					
1.14.	ITT	IDSL_MH4	Summary of Current Medical Conditions		SAC
1.15.	ITT	IDSL_MH4	Summary of Past Medical Conditions		SAC
1.16.	ITT	IDSL_SP07	Summary of Family History of Cardiovascular Risk Factors		SAC
1.17.	ITT	IDSL_SP08	Summary of COPD History and COPD Exacerbation History at Screening		SAC
1.18.	ITT	IDSL_SP10	Summary of Smoking Status		SAC
1.19.	ITT	IDSL_SP11	Summary of COPD Medications		SAC
1.20.	ITT	IDSL_CM1	Summary of Non-COPD Medications		SAC

**10.10.5. Efficacy Tables**

Overall Summary of Errors					
No.	Population	IDSL / TST ID / Example Shell	Title	Programming Notes	Deliverable
2.01	ITT	EFF_T01	Summary of Errors on ELLIPTA		SAC
2.02	ITT	EFF_T01	Summary of Errors on DISKUS + HandiHaler	Page by DISKUS + HandiHaler Errors, DISKUS Errors and HandiHaler Errors	SAC
2.03	ITT	EFF_T06	Summary of Overall Errors		SAC
2.04	ITT	EFF_T06	Summary of Overall Errors by Age	Use age categories: 40-64, 65-74 and $\geq 75$ .	SAC
2.05	ITT	EFF_T06	Summary of Critical Errors		SAC
Primary Efficacy Tables					
Percentage of Overall Errors					
2.06	ITT	EFF_T04	Analysis of Percentage of Participants making Zero Errors after 28 days use (Primary Estimand: Principle Strata)		SAC
2.07	ITT	EFF_T04	Analysis of Percentage of Participants making Zero Errors after 28 days use (Supplementary Estimand: Composite)		SAC
2.08	ITT	EFF_T09	Tipping Point Analysis of Participants making Zero Errors after 28 days use (Supplementary Estimand: Composite)		SAC
2.09	ITT	EFF_T07	Sensitivity Analysis of Percentage of Participants making Zero Errors after 28 days use (Primary Estimand: Principle Strata)		SAC

Overall Summary of Errors					
No.	Population	IDSL / TST ID / Example Shell	Title	Programming Notes	Deliverable
2.10	ITT	EFF_T07	Sensitivity Analysis of Percentage of Participants making Zero Errors after 28 days use (Supplementary Estimand: Composite)		SAC
Secondary Efficacy Tables					
Percentage of Critical Errors					
2.11	ITT	EFF_T04	Analysis of Percentage of Participants making Zero Critical Errors after 28 days use (Primary Estimand: Principle Strata)		SAC
Number of Overall Errors					
2.12	ITT	EFF_T01	Summary of Number of Errors by Type for each Inhaler after 28 Days of Use	Replace 'Early withdrawal' column with 'Difference (ELLIPTA minus DISKUS + HandiHaler)	SAC
2.13	ITT	EFF_T08	Summary of Number and Change in Errors per Participant for each Treatment Group (V2 and V3) after 28 Days of Use		SAC
2.14	ITT	EFF_T08	Summary of Number and Change in Errors for each Treatment Group in Participants with One or more Errors after 28 Days of Use		SAC
Exploratory Efficacy Tables					
Preference Attributes					
2.15	ITT	EFF_T04	Analysis of Percentage of Participants with Zero Errors after 28 Days of Use, including the Number of Prescribed Maintenance Inhalers as a Covariate.		SAC
2.16	ITT	EFF_T04	Analysis of Percentage of Participants with Zero	Include an additional row for	SAC

Overall Summary of Errors					
No.	Population	IDSL / TST ID / Example Shell	Title	Programming Notes	Deliverable
			Errors after 28 Days of Use, including the Number of Prescribed Maintenance Inhalers as a Covariate (Interaction Model).	the p-value of the interaction between number of prescribed maintenance Inhalers and treatment option.	
2.17	ITT	EFF_T04	Analysis of Participants making Zero Errors after Reading the PIL (s) at the Start of Each Treatment Period.		SAC
2.18	ITT	EFF_T03	Summary and Analysis of Treatment Preference		SAC
2.19	ITT	EFF_T03	Summary of Treatment Preference by Age	This is a summary table only so do not include any analysis. Use age categories: 40-64, 65-74 and $\geq 75$	SAC

**10.10.6. Safety Tables**

No.	Population	IDSL / TST ID / Example Shell	Title	Programming Notes	Deliverable
Adverse Events					
3.01	ITT	IDSL_AE1	Summary of Adverse Events		SAC
3.02	ITT	IDSL_AE1	Summary of On-Treatment Adverse Events		SAC
3.03	ITT	IDSL_AE1	Summary of Post-Treatment Adverse Events		SAC
3.04	ITT	IDSL_AE1	Most Common Non-Serious Drug Related Adverse Events	> 3 %	SAC
3.05	ITT	IDSL_AE1	Summary of Serious Adverse Events		SAC
3.06	ITT	IDSL_AE1	Summary of Serious Drug Related Events		SAC
3.07	ITT	IDSL_AE1	Most Common Serious Drug Related Adverse Events	> 3 %	SAC
3.08	ITT	IDSL_AE1	Summary of Fatal Adverse Events		SAC
3.09	ITT	IDSL_AE1	Summary of Non-Fatal Serious Adverse Events		SAC
3.10	ITT	IDSL_AE1	On-treatment AEs leading to Discontinuation of Study Treatment or Withdrawal from the Study		SAC
3.11	ITT	SAFE_T01	Summary of On-Treatment Moderate/Severe COPD Exacerbations		SAC
3.12	ITT	SAFE_T01	Summary of Post-Treatment COPD Moderate/Severe Exacerbations		SAC
3.13	ITT	IDSL_AE1	Summary of Serious Adverse Events by System Organ Class and Preferred Term (Number of Subjects and Occurrences)		SAC

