3.3.1. Risk Assessment

Potential Risk of Clinical Significance	Summary of Data/Rationale for Risk	Mitigation Strategy
Paradoxical bronchospasm, which may occur with an immediate increase in wheezing after inhaling.	As with other inhalation therapy, paradoxical bronchospasm may occur with an immediate increase in wheezing after dosing. From post-marketing data, paradoxical bronchospasm has been reported at a frequency of <1/10,000 including isolated reports.	This should be treated immediately with a fast and short acting inhaled bronchodilator. Investigators will be instructed to assess the participant's condition to determine their eligibility to continue in the study and the need for alternative therapy.
Allergic reaction due to hypersensitivity to placebo excipients.	The placebo inhalers and placebo capsules (for HandiHaler) contain the excipient lactose and lactose blended with magnesium stearate. There are known allergies to these ingredients.	Participants with a know hypersensitivity to any of these, or severe milk protein allergy that could contraindicate study participation are excluded from the study (Section 6.2). If an allergic reaction occurs, it should be treated immediately with a fast and short acting inhaled bronchodilator and other appropriate drugs used in allergic reactions (e.g. glucocorticosteroids, adrenalin) guided by the nature and severity of the allergic reaction. Investigators will be instructed to assess the participant's condition to determine their eligibility to continue in the study and the need for alternative therapy.

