10.2. Sample Size Determination

The sample size calculations for this study have been based on the primary endpoint, which is the percentage of participants making zero errors in each treatment group (ELLIPTA or DISKUS + HandiHaler) after 28 days use.

The estimates of inhaler errors were taken from the overall errors reported in the 200301 study for each individual inhaler (ELLIPTA, DISKUS and HandiHaler) separately. Although this study is only assessing combined errors in the DISKUS + HandiHaler treatment group, individual inhaler errors were used to estimate the combined error rate in order to provide a conservative estimate. By doing this it assumes that participants, who made no errors on the DISKUS inhaler, would not make any errors of the HandiHaler inhaler and vice-versa.

As the 200301 study only had a single visit, no estimates were available for error rates over 28 days, however the study did provided estimates of participant errors after reading the PIL and after being instructed on correct use by a HCP up to three times. As participants will have the PIL for 28 days, and can be instructed by a HCP at the inhaler dispensing visit if necessary, both estimates of error rates along with a sensitivity analysis examining some of the potential error rates between were used to inform sample size calculations.

Using 10,000 simulations, a total of 216 participant (54 per treatment sequence) provide at least 90% power to show a statistically significance difference between the overall error rate of the ELLIPTA inhaler versus DISKUS + HandiHaler inhalers, for all of the paired treatment error rates shown in [Table 1](#).

Table 1 Error rates of ELLIPTA vs. DISKUS + HandiHaler achievable with 90% power, 5 % Type 1 error using a total of 216 participants

ELLIPTA Error Rate	DISKUS + HandiHaler Error Rate
33%	>=50%
30%	>=47%
20%	>=35%
10%	>=23%
5%	>=15%

Conditional logistic regression and a two-sided 5% significance level were used as the analysis method for all simulations performed. As it is expected that some participants would drop out or change inhalers during the study, with 10% withdrawal it would be

necessary to enrol 240 participants (60 per treatment sequence) to ensure there were 216 participants with evaluable data at the end of the study.

For the purpose of this study an evaluable participant is defined as a randomized participant who completed error assessments for both randomized treatment groups.

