10.4.2. Safety Analyses

All safety analyses will be performed on the Safety Population.

Adverse events (AEs) will be coded using the standard GSK dictionary, Medical Dictionary for Regulatory Activities (MedDRA), and grouped by body system. The number and percentage of participants experiencing at least one AE of any type, AEs within each body system and AEs within each preferred term will be presented for each treatment group. Separate summaries will be provided for all AEs, drug related AEs, fatal AEs, non-fatal SAEs, AESIs and AEs leading to withdrawal.

Deaths and SAEs, if applicable, will be documented in case narrative format.

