### 8.1. Adverse Events Analyses

Adverse events analyses including summaries of adverse events (AEs), Serious (SAEs) and other significant AEs will be based on GSK Core Data Standards. As this is a placebo only device study and no active drug is prescribed, summaries will be provided for all participants combined regardless of their randomised treatment sequence. The details of the planned displays are provided in [Appendix 10: List of Data Displays](#).

A summary of the following AEs and SAEs will be provided:

- Any AE (pre treatment (SAE only)-, on- treatment or post-treatment)
- Any on-treatment drug related AE

- Any AE (pre-treatment or on-treatment) leading to permanent discontinuation of study treatment or withdrawal from study
- Any non-fatal SAE
- Any fatal SAE
- Any on-treatment non-fatal drug related SAE
- Any on-treatment fatal drug related SAE

AE incidence will be summarised overall using the primary System Organ Class (SOC) and preferred term. All listings of AEs/SAEs will identify whether each adverse event occurred pre-treatment, on treatment or after treatment.

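### The promised summary of drug-related AEs has no matching table: non-serious related events appear only in a table cut off at > 3 %

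*SAP*

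**What the plan says.** Protocol 10.4.2 sets out the safety outputs: "Separate summaries will be provided for all AEs, drug related AEs, fatal AEs, non-fatal SAEs, AESIs and AEs leading to withdrawal". Drug-related AEs are a category of their own there, with no minimum frequency.

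SAP 8.1 takes this up under the lead-in "A summary of the following AEs and SAEs will be provided", and one of the items is "Any on-treatment drug related AE". That is slightly narrower than the protocol because it is confined to the on-treatment phase, but it too has no threshold. The same section pools all participants for the AE summaries, says incidence will be shown by system organ class and preferred term, and sends the reader to Appendix 10 for the displays. SAP 2.1 declares no departure from the analysis planned in the amended protocol.

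The display list in SAP 10.10.6 has three tables defined by relatedness:

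- Table 3.04, "Most Common Non-Serious Drug Related Adverse Events", with the programming note > 3 %
- Table 3.06, "Summary of Serious Drug Related Events", with no cut-off
- Table 3.07, "Most Common Serious Drug Related Adverse Events", with the note > 3 %

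Tables 3.01 (all AEs) and 3.02 (on-treatment AEs) have no cut-off but are not defined by relatedness. Listing 09 gives all AEs by subject.

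**The concern.** The text promises a complete count of related events, but the list the tables will be produced from supplies only part of it. Serious related events are fully covered. Non-serious ones are tabulated as related only if they pass a frequency filter that neither the protocol nor SAP 8.1 mentions and that SAP 2.1 does not declare as a change.

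This matters more here than a missing table usually would. The study gives no active drug, so the events judged related are the ones that bear on the devices and their excipients. Protocol 3.3.1 names two such risks, paradoxical bronchospasm and allergic reaction to excipients, and says of the first that "paradoxical bronchospasm has been reported at a frequency of <1/10,000 including isolated reports". A table restricted to common events is a poor vehicle for infrequent reactions. As listed, the tables would not let a reader of the study report see which non-serious events the investigators considered related, unless those events were common.

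**Working it through.** **Inputs**

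- Evaluable target 216, withdrawal 10%, enrolment 240: Protocol 10.2.
- One pooled denominator for AE summaries: SAP 8.1. The safety population equals the ITT population: SAP section 4.
- Cut-off > 3 % for Tables 3.04 and 3.07: SAP 10.10.6.
- Assumed, because the SAP does not say: the cut-off is applied to each preferred term, and to the unrounded percentage.

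**Step 1: reproduce the planned denominator.** 216 / (1 − 0.10) = 240, which agrees with Protocol 10.2.

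**Step 2: match the promise to the displays.**

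| Table | Events covered | Defined by relatedness? | Cut-off |
|---|---|---|---|
| 3.01 | all | no | none |
| 3.02 | on-treatment | no | none |
| 3.04 | non-serious | yes | > 3 % |
| 3.06 | serious | yes | none |
| 3.07 | serious | yes | > 3 % |

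No row is defined by relatedness, covers non-serious events and has no cut-off. Table 3.07 is a subset of Table 3.06 and adds nothing to coverage.

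**Step 3: size of the omitted range.** 0.03 × 240 = 7.2.

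- 7/240 = 2.92%, not above 3%, so the term is left out.
- 8/240 = 3.33%, above 3%, so the term is printed.

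A non-serious related term in 1 to 7 participants is therefore missing from the related-event tables.

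**Step 4: sensitivity to the assumptions.** The largest omitted count is the whole-number part of 0.03 × N.

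- N = 216 gives 6.48 and N = 233 gives 6.99, so the maximum is 6 from 216 to 233.
- N = 234 gives 7.02 and N = 266 gives 7.98, so the maximum is 7 from 234 to 266.
- If percentages were rounded to whole numbers before the filter, 8/240 would become 3% and also drop out. The first term printed would then have 9 participants (3.75%, rounded to 4%).

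**Step 5: illustration with assumed incidences.** The 1% and 2% rates below are not in the documents. They only show how the filter behaves for X ~ Binomial(240, p).

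- p = 1%: P(X ≥ 1) = 1 − 0.99^240 = 0.910; P(X ≥ 8) = 0.003.
- p = 2%: P(X ≥ 1) = 1 − 0.98^240 = 0.992; P(X ≥ 8) = 0.111.

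The only rate the documents give is the post-marketing bound of 1 in 10,000 for paradoxical bronchospasm. If that is read as a per-participant risk (again an assumption), P(X ≥ 1) is at most 1 − 0.9999^240 = 0.024.

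**Step 6: what the fix changes.** With no threshold, a related term is printed from 1/240 = 0.42% instead of from 8/240 = 3.33%.

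**The case against.** The strongest reply is that almost nothing is hidden. Tables 3.01 and 3.02 have no threshold, and SAP 8.1 has AE incidence shown by preferred term, so a single non-serious bronchospasm or allergic reaction would be tabulated. Listing 09 carries it too, and an on-treatment event that led to withdrawal would be in Table 3.10. Serious related events are all in Table 3.06, and Protocol Appendix 3 gives intensive emergency-room or home treatment for allergic bronchospasm as an example of a serious event. The graver forms of the named risks would therefore be shown as related. All of this stands, and it confines the point to the attribution of non-serious events.

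A reader might infer something stronger: that a related reaction would be visible only in the subject listing, or that the cut-off suppresses just the rare reactions named in Protocol 3.3.1. The documents do not support either. The first overlooks Tables 3.01, 3.02 and 3.06. On the second, at the documented bronchospasm rate the chance of even one case among 240 is at most about 2.4%, so an unthresholded table would very probably show no bronchospasm either. Nor is it safe to say that an empty Table 3.04 would be taken as no related events, since its title says that it covers only the most common ones.

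It can also be said that the commitment in SAP 8.1 still stands, so this is a mismatch between text and display list. That is a fair description, but it does not dispose of the point. SAP 8.1 defers to the display list, and that list contains an explicit filter that would withhold part of a promised result.

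**Conclusion.** The point holds as a gap between a stated safety analysis and the tables planned to deliver it. Both documents promise an unthresholded summary of drug-related AEs (on-treatment in the SAP), and SAP 10.10.6 provides it only for serious events. With a per-term cut-off on unrounded percentages and about 240 participants in the ITT population, a non-serious related term in 1 to 7 participants is identified as drug-related in no summary table. The upper limit is 6 if the population is between 216 and 233.

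No data are lost, the events remain in the general AE tables and in Listing 09, and no endpoint, estimate or test is affected. It is still worth correcting, because relatedness is the attribute of most interest in a placebo-device study and the repair is small.

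**What to change.** Add to SAP 10.10.6 a summary of on-treatment drug-related AEs by system organ class and preferred term, for all participants combined and with no frequency threshold. Table 3.04 may stay as an additional common-event display; if it does, its note should say what the > 3 % applies to. If the sponsor prefers the thresholded table as the only summary of non-serious related events, SAP 8.1 should say so, and SAP 2.1 should record and justify the departure from Protocol 10.4.2.

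The cost is one extra table from data already collected, using the same standard AE shell as the neighbouring tables. No protocol amendment is needed.

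Two optional tidying steps fit the same edit. Table 3.07 could be removed because it repeats part of Table 3.06. The title of Table 3.10, which covers on-treatment events only, could be aligned with SAP 8.1, which also includes pre-treatment events leading to discontinuation or withdrawal. Neither is part of the main point: pre-treatment collection is limited to serious events, and the subject listings of AEs leading to withdrawal would show any such case.

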**10.10.7. Efficacy Figures**

Primary Efficacy Analysis					
No.	Population	IDSL / TST ID / Example Shell	Title	Programming Notes	Deliverable
2.1	ITT	EFF_F01	Percentage of Participants with Zero Errors and Zero Critical Errors by Treatment Group		SAC

**10.10.8. ICH Listings**

ICH : Listings					
No.	Population	IDSL / TST ID / Example Shell	Title	Programming Notes	Deliverable
Study Population: Subject Disposition and Demography					
01	ASE	IDSL_ES7	Listing of Screen Failures		SAC
02	ITT	IDSL_ES2	Listing of Reasons for Study Withdrawal		SAC
Study Population: Protocol Deviations					
03	ITT	IDSL_SP01	Listing of Important Protocol Deviations		SAC
04	ASE	IDSL_IE3	Listing of Inclusion/ Exclusion/ Randomisation Criteria Deviations		SAC
Study Population: Treatment					
05	ITT	IDSL_TA1	Listing of Randomised and Actual Treatment Sequence		SAC
Study Population: Demography					
06	ITT	IDSL_DM2	Listing of Demographic Characteristics	Include BMI as the optional	SAC

ICH : Listings					
No.	Population	IDSL / TST ID / Example Shell	Title	Programming Notes	Deliverable
				measurement. In addition, include a country column as the first sort variable.	
07	ITT	IDSL_DM9	Listing of Race	Include a country column as the first sort variable.	SAC
Safety: Adverse Events					
08	ASE	IDSL_AE7	Listing of Subject Numbers for Individual Adverse Events		SAC
09	ASE	IDSL_AE8	Listing of All Adverse Events	ICH E9	SAC
10	ASE	IDSL_AE8	Listing of All Serious Adverse Events	ICH E9	SAC
11	ASE	IDSL_AE14	Listing of Reasons for Considering as a Serious Adverse Event	ICH E9	SAC
12	ASE	IDSL_AE8	Listing of Non-Serious Adverse Events Leading to Withdrawal from Study / Permanent Discontinuation of Study Treatment	ICH E9	SAC
13	ASE	IDSL_AE8	Listing of Serious Adverse Events Leading to Withdrawal from Study / Permanent Discontinuation of Study Treatment	ICH E9	SAC
Efficacy: Primary Endpoint					
14	ITT	EFF_L01	Listing of Subject Errors		SAC

